8.2. Laboratory assessment

8.2.1. Xpert MTB/RIF Ultra

Ultra testing will be done at the trial laboratory on standard GeneXpert platforms for the two respiratory samples and the two stools samples.

The Ultra assay will be carried out according to the manufacturers' guidelines and will be defined as positive, negative or indeterminate based on the manufacturers' recommended criteria.

Results will be interpreted as follows:

- In case of positive result for the presence of MTB (including "trace call" positive result) on any
 respiratory sample or stool sample processed with the sucrose flotation method, the global result
 will be given as "MTB detected".
- In case of negativity of Ultra performed on the two respiratory samples and the two stool samples processed with the sucrose flotation method, the global result will be given as "MTB not detected".
- In case of an invalid or error result for MTB detection, the test will be repeated if sample volumes allow for it.
- In case of rifampicin resistance detected on one or more sample, the result will be given as "MTB detected, rifampicin resistance detected". Otherwise the result will be given as "MTB detected, rifampicin resistance not detected (or indeterminate)". Children with rifampicin resistance detected by Ultra will have culture and phenotypic DST performed on leftovers from stool and respiratory samples (with additional samples taken if needed), and will be started on empirical MDR-TB treatment according to national guidelines.

Xpert Ultra results will be communicated to the study nurse by message by the laboratory technician and to the treating physician as soon as available. If positive, TB treatment will be initiated immediately.

For stools, only Ultra results from stools processed with the sucrose flotation method will be communicated to the clinician as this is the only method published and validated in a clinical study. Results from Ultra assay on stools processed with the SPK, STEP method and sucrose flotation optimized method will not be disclosed.

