3.3. Reference diagnosis/case definition for the study and validation by the Expert Committee

For the secondary endpoint of the evaluation of the accuracy of the Ultra test on stool against the TB composite reference standard, children will be classified into 3 categories, according to the updated Clinical Case Definitions for Classification of Intrathoracic Tuberculosis in Children, detailed in Table 2: *confirmed*, *unconfirmed*, or *unlikely* tuberculosis or any subsequent published update at the time of final case review if feasible and approved by the Scientific Advisory Board (SAB). Classification will be done by an expert committee set up for the TB-Speed HIV and TB-Speed SAM studies.

Case definition	Refined criteria
Confirmed tuberculosis	Bacteriological confirmation obtained (Mycobacterium tuberculosis confirmed by culture or Xpert MTB/RIF assay from at least 1 respiratory specimen)
	Bacteriological confirmation NOT obtained AND at least 2 of the following:
	 Symptoms/signs suggestive of tuberculosis¹
	CXR consistent with tuberculosis ²
Unconfirmed tuberculosis	Close tuberculosis exposure or immunologic evidence of M. tuberculosis infection
	 Positive response to tuberculosis treatment (requires documented positive clinical response on tuberculosis treatment—no time duration specified)
	AND no spontaneous improvement of symptoms in the absence of antituberculosis treatment
Unlikely	Bacteriological confirmation NOT obtained AND criteria for "unconfirmed tuberculosis" NOT met
tuberculosis	(including spontaneous improvement of symptoms in the absence of antituberculosis treatment)

Table 2. Updated Clinical Case Definition for Classification of Intrathoracic Tuberculosis in Children (adapted from Graham et al, 2015 [42])

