An Expert Committee will be set up at national level for the purpose of case review and validation of TB diagnosis. The Expert Committee will not review all cases systematically. In agreement with the SAB, the Expert Committee will not review cases which are Ultra (bacteriologically)-confirmed TB cases, or true negative TB (Ultra-negative untreated children alive at 2 months with normal M2 follow-up CXR). The Expert Committee will review remaining cases, which are neither Ultra-confirmed TB nor true negative TB considering the following parameters: initial clinical and follow up data, microbiological data and radiological features.

The Expert Committee will classify children using the Revised Classification of Intrathoracic Tuberculosis Case Definitions for Diagnostic Evaluation Studies in Children (see Table 2 above), following Standard Operating Procedures (SOPs) specifically developed for the study. A centralized Expert Committee will review part of all cases reviewed at country level to ensure homogeneity of classification across countries.

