11.2.2. Analysis of secondary endpoints

- Per-protocol analysis of sensitivities and specificities of Ultra on stool using TB culture reference standard (LJ ans MGIT) in respiratory sample, excluding invalid Ultra results, contaminated and NTM culture results from analysis. Regarding contamination, since two culture methods will be used per respiratory sample (LJ and MGIT), to be excluded both culture results per sample will need to be contaminated.
- Head to head comparison of the sensitivities and specificities between the different stool processing methods using culture reference standard and McNemar test for matched data:
 - Sucrose flotation classic method vs Sucrose Flotation optimised method
 - Sucrose flotation classic method vs SPK method
 - Sucrose flotation classic method vs STEP method
 - Sucrose flotation optimised method vs SPK method
 - Sucrose flotation optimised method vs STEP method
 - SPK method vs STEP method
- Head to head comparison of the sensitivities and specificities between the different stool processing methods using the TB composite reference standard as defined by Clinical Case Definition for Classification of Intrathoracic Tuberculosis in Children, and McNemar test for matched data:
 - Sucrose flotation classic method vs Sucrose Flotation optimised method
 - Sucrose flotation classic method vs SPK method
 - Sucrose flotation classic method vs STEP method
 - Sucrose flotation optimised method vs SPK method
 - Sucrose flotation optimised method vs STEP method
 - SPK method vs STEP method
- Description of results for rifampicin resistance using stool Ultra, respiratory Ultra, LPA and DST
- Agreement of the different stool sample processing methods for Ultra detection head to head using Kappa analysis.
- Comparison of the proportion of rifampicin resistance indeterminate Ultra test results between different stool processing methods using McNemar test for matched data.
- Comparison of the proportion of invalid Ultra test results between different stool processing methods using McNemar test for matched data.
- Comparison of the proportion of Ultra results "trace" between the methods using McNemar test for matched data.
- Proportion of very low, low, medium and high Xpert Ultra results by different methods

- Change in sensitivity and specificity at patient level by using 2 stools vs using just the 1st stool specimen for each processing method.

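### The composite reference standard depends on the one stool result that clinicians see, which favours standard sucrose flotation in three secondary head-to-head comparisons

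*Protocol*

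**What the plan says.** **Disclosure (Protocol 8.2.1).** With a positive, trace calls included, on any "respiratory sample or stool sample processed with the sucrose flotation method, the global result" is reported as MTB detected. The section continues: "If positive, TB treatment will be initiated immediately". Among stool results the clinician sees one method only: "For stools, only Ultra results from stools processed with the sucrose flotation method will be communicated to the clinician". For the rest: "Results from Ultra assay on stools processed with the SPK, STEP method and sucrose flotation optimized method will not be disclosed".

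**Composite standard (3.3, Table 2).** *Confirmed* TB must be "confirmed by culture or Xpert MTB/RIF assay from at least 1 respiratory specimen". *Unconfirmed* TB needs at least two of four criteria, one of which is "Positive response to tuberculosis treatment (requires documented positive clinical response on tuberculosis treatment", and no improvement while untreated. *Unlikely* TB includes children who improve without treatment.

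**Committee review (3.3).** By agreement "the Expert Committee will not review cases which are Ultra (bacteriologically)-confirmed TB cases, or true negative TB". True negatives are Ultra-negative, untreated, alive at 2 months and with a normal chest X-ray. The specimen behind Ultra-confirmed and Ultra-negative is not named. All other children are reviewed on clinical, follow-up, microbiological and radiological data. The X-ray readers are blinded to clinical information. Nothing in the protocol blinds the Committee to stool results.

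**Use (2.2 and 11.2.2).** Confirmed and unconfirmed TB together form the composite target. Six pairwise McNemar comparisons of sensitivity and specificity are made "using the TB composite reference standard as defined by Clinical Case Definition for Classification of Intrathoracic Tuberculosis in Children". Three of the six involve standard sucrose flotation.

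**The concern.** A reference standard for a head-to-head comparison should not depend on one of the methods compared. Here a child with negative respiratory results and a positive standard-flotation stool is treated. That child can no longer be an untreated true negative, can no longer improve without treatment, and can gain the treatment-response criterion. The same child positive only on SPK, One-step or optimised flotation gets none of this, and if finally classed as unlikely counts as that method's false positive.

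The treatment route matters because the entry criteria in section 5.1.1 (cough, fever, failure to thrive, suggestive X-ray) largely overlap the symptom and X-ray criteria of Table 2. Many children hold one criterion at enrolment, so a recorded response to treatment can supply the second.

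At stake is the relative standing of the methods. The Rationale keeps standard flotation as the benchmark for the optimised version, and section 4.1 aims the results at WHO recommendations. A tilted composite could make three centrifuge-free methods look less accurate than they are.

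**Working it through.** The plan gives no figure for this, so there is none to reproduce. The question is how the disclosed result passes through the classification, and how large the effect could be.

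**Tracing one child.** Take a respiratory-negative child with exactly one Table 2 criterion at enrolment.

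- Positive only on standard flotation: reported as MTB detected, treated, not a true negative, sent to the Committee with microbiological data that may include the stool result. If improvement is recorded as treatment response, the child has two criteria and is *unconfirmed*, a true positive for flotation.
- Positive only on a hidden method: no report and no treatment on that account. If the child improves, the class is *unlikely*, a false positive for that method.

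**Inputs for the illustration**

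- True specificity: 90% (section 4.3, planning value) and 99% (section 4.1, stool Xpert MTB/RIF). The 97% row takes 2 points off 99%, the specificity loss that section 1 reports for Ultra in children. The 95% row is intermediate.
- Stage 1 children without respiratory confirmation: 160, about 177 less 10% (section 4.3).
- Confirmed cases: 16 + 97 = 113 (section 4.3), with 60% stool sensitivity.
- Assumptions not in the protocol: 25% of the 160 truly unconfirmed (40 children, leaving 120 unlikely); 10% stool sensitivity in those 40; and the hidden method copies the disclosed result with probability 0.3 in the 160, otherwise independent.
- q, the share of flotation-positive unlikely children moved to *unconfirmed*: unknown, so run at 0, 0.5 and 1.

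**Formulas.** Let f = 1 − true specificity, equal for both methods, and c = 0.3 + 0.7f, the chance that the hidden method is positive when flotation is.

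- Apparent specificity, flotation: 1 − f(1 − q)/(1 − fq)
- Apparent specificity, hidden method: 1 − f(1 − qc)/(1 − fq)

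Example with f = 0.10, q = 0.5, c = 0.37: flotation 1 − 0.05/0.95 = 94.7%; hidden 1 − 0.0815/0.95 = 91.4%. At q = 1 flotation is always 100% and the hidden method is 1 − 0.7f.

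| True specificity | q | Flotation | Hidden method | Exact McNemar p < 0.05 (simulation, 4,000 runs) |
|---|---|---|---|---|
| 90% | 0 | 90.0% | 90.0% | 3.1% |
| 90% | 0.5 | 94.7% | 91.4% | 12.1% |
| 90% | 1 | 100% | 93.0% | 76.0% |
| 95% | 0.5 | 97.4% | 95.7% | 4.3% |
| 95% | 1 | 100% | 96.5% | 20.8% |
| 97% | 1 | 100% | 97.9% | 4.1% |
| 99% | 0.5 | 99.5% | 99.1% | about 0% |
| 99% | 1 | 100% | 99.3% | about 0% |

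The rejection rates follow from the discordant pairs. At q = 1 these all go one way, and their expected number is 120 × 0.7f(1 − f): 7.6 at 90% and 0.8 at 99%. An exact McNemar test needs at least 6:0 (2 × 0.5^6 = 0.031; 5:0 gives 0.0625).

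**Sensitivity.** With q = 0 both methods show (113 × 0.6 + 40 × 0.1)/153 = 71.8/153 = 46.9%. At 90% specificity and q = 1, 12 children move: flotation (71.8 + 12)/165 = 50.8%, hidden (71.8 + 12 × 0.37)/165 = 46.2%. At 99% and q = 1 the simulation gives 47.4% against 46.9%.

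**The case against.** The strongest reply has four parts.

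1. *Stool Ultra is not a criterion of the case definition.* This stands. A reader might infer from the MTB-detected label and the unspecified Ultra-confirmed wording that a stool-only positive child enters as *confirmed*. Table 2 limits confirmation to respiratory specimens, and section 3.3 says the same of culture-negative children with positive Ultra. What remains is the indirect route through treatment, plus what the Committee may see.
2. *The route is conditional.* This stands in part. Children who already hold two criteria are *unconfirmed* whatever the stool shows, and losing true-negative status only sends a child to review. Only children short of two criteria can move, and response must be documented.
3. *The scope is narrow.* This stands. Enrichment children are already respiratory Xpert positive.
4. *The 90% is a planning value.* Section 4.1 cites 99%, and Table 1 gives 242/243 = 99.6% for centrifuged flotation. Both are for Xpert MTB/RIF, however, and section 1 reports lower specificity with Ultra, so neither settles the value for Ultra on stool.

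A reader might also object that the true-negative shortcut does not ask for negative culture. That gap is minor: section 4.2 gives culture results to clinicians, so a culture-positive child would seldom remain untreated.

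Committee procedures are left to SOPs that are not at hand and may already withhold stool results. Section 3.3 does not say so, and withholding them would not remove the treatment route.

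**Conclusion.** The point holds for a limited part of the plan. The composite standard depends on one of the four methods and not on the others, and in every scenario run with reclassification (q above 0) the error favours standard flotation. It touches three of six pairwise comparisons in one secondary analysis, essentially through stage 1 children without respiratory confirmation.

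Its size is not known. Under the stated assumptions the spurious specificity gap runs from 0.4 to 0.7 points at 99% (q of 0.5 to 1) to 3.3 to 7.0 points at 90%. The spurious sensitivity gap reaches 4.6 points at most. The q = 1 rows are upper bounds, not expectations.

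A reader might infer that the main results are compromised. They are not: the primary accuracy and the culture-based head-to-head tests use respiratory culture alone. The matter should still be settled before children are classified, because a classification made with stool results in view is hard to undo.

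**What to change.** In section 3.3 and the Committee SOP:

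1. State that Ultra-confirmed and Ultra-negative refer to respiratory specimens only, in line with Table 2.
2. Withhold all stool Ultra results, and the global result that contains one, from the Expert Committee when it classifies for this study.
3. Keep the published case definition for the main composite analysis. Add a sensitivity analysis for children treated solely on the disclosed stool result, either excluding them or disregarding their treatment response.

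Of the two versions in step 3 the second is more informative. Exclusion takes flotation's own positives out of the *unlikely* group, so for specificity it reproduces the q = 1 rows above. Disregarding response can err the other way, since a child with real TB treated on flotation alone may fall to *unlikely*. That is why it belongs in a sensitivity analysis and not in the main classification.

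Disclosure to clinicians and the treatment rules are left as they are. The cost is some wording, one filtered field in the Committee dossier and one extra analysis. Because the Committee also serves the HIV and SAM studies, the filter should be specified for this study's classification only.

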8.2.2. Mycobacterial culture

Culture will be done at the trial laboratory on two respiratory samples (ES or GA). Mycobacterial culture will be done in liquid medium (MGIT) by an automated method (BACTEC 960), and on solid media (Lowenstein Jensen) if available. Identification of mycobacteria will be done by the molecular method Gen-Probe, or Niacin test, or MPT64 antigen test depending on availability at the laboratory level. Detection of TB drug

resistance will be performed using first-line drug sensibility testing (DST) on liquid media (MGIT) or solid media or line probe assays (LPA).

8.2.3. HIV testing

HIV serology will be performed at inclusion if not available in the patient medical chart, according to national routine practices. HIV testing in children aged less than 18 months will be based on an HIV RNA or DNA nucleic acid amplification tests (PCR).

8.2.4. Laboratory quality control

Internal Quality Control (QC) will be routinely performed for Ultra testing, including calibration tests and procedures provided by the manufacturer. Internal QC results and logs will be available for monitoring.

Procedures for laboratory quality assurance will be detailed in study-specific SOPs.

8.3. Radiological assessment

A chest radiograph anteroposterior and lateral view in children below 5 years old will be performed using standard analogue X-ray machines at visits D0 and M2.

9. STUDY VIGILANCE

9.1. Definitions

> Adverse events

An "adverse event" (AE) is defined as any unfavourable, expected or unexpected sign (clinical or biological) occurring during the study in a human subject participating in the research, whether or not considered related to treatment or procedures or to participation in the study.

Serious adverse events

A "serious adverse event" (SAE) (ICH-E6 step 4. 1996) refers to any untoward medical occurrence that:

- Results in death;
- Is life-threatening (meaning that the subject was at immediate risk of death at the time of the event; it does not refer to an event which hypothetically might have caused death if it were more severe);
- Requires hospitalization or prolongation of existing hospitalization;
- Results in persistent or significant disability or incapacity;
- Is a congenital anomaly or birth defect.
- Is an "important medical event" (medical events, based upon appropriate medical judgment, which may jeopardize the subject or may require medical or surgical intervention to prevent one of the above characteristics/consequences). Examples: allergic bronchospasm requiring intensive treatment at an emergency room or at home, blood dyscrasias, convulsions that do not result in inpatient hospitalization.

➢ New fact

A new fact is defined as any safety data that could significantly modify the evaluation of the benefit/risk evaluation of the research or the study product, likely to affect the safety of participants or that could modify the study product administration, the study documentation or the conduct of the study, or to suspend or interrupt or modify the protocol or similar studies.

➢ Severity

The severity of an AE will be graded using the "Division of AIDS table for grading the severity of adult and paediatric adverse events" (Version 2.1 – July 2017) as included in the SOPs [69].

➤ Causality

"Causality" refers to causal relationship between a specific AE, the study intervention and any other concomitant intervention/medication.

9.2. Expected adverse events related to the study intervention

Both GA and sputum collection are components of routine practice in the two hospitals participating in the study. They are recommended by WHO for paediatric presumptive TB sample collection. No AE is expected from sputum collection but vomiting can occur with GA.

No AEs are expected from stool sample collection.

9.3. Reporting of adverse events

There will be no systematic reporting of other AEs in the study.

9.4. Notification of serious adverse events

In this diagnostic study without investigational medicinal product, and with very low expected risk of AEs linked to the intervention, there will be no systematic notification of SAEs to the sponsor at the exception of:

- Death;
- Life-threatening AEs, excluding asymptomatic biological AEs of grade 4

For children participating in both TB-Speed HIV/SAM studies and the TB-Speed stool-processing study, only one SAE will be notified in one SAE report with the mention that the child is enrolled in both studies.

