For children identified from the routine practice in the two hospitals, the nurse will collect two respiratory samples (sputum or GA) in consecutive children with presumptive TB to be tested using Ultra as done in routine care, record symptoms and refer the child for clinical exam and for chest X-ray. For the purpose of the study, two stool samples will be collected to be tested with Ultra. In addition, for study purpose the two respiratory samples will be tested with Mycobacterial culture as this test is not routinely prescribed for TB diagnosis in the study sites. However, culture results will be made available to the clinicians for case management. HIV-testing will be offered for children with unknown status as done under routine practice in both sites.

Xpert positive enrichment cohort:

Any child with presumptive TB and a positive Xpert result (MTB/Rif or Ultra according local practice) from one respiratory sample (NPA, IS or GA) will be proposed to participate in the study.

If the child is enrolled in the TB-Speed SAM or HIV studies, the study nurse will then collect two stool samples as well as information about the clinical examination, chest X-ray, HIV-testing and the mycobacterial culture

results from respiratory samples as soon as they are available, from the data collected in the TB-Speed records since all these procedures are already performed in these studies.

For children identified from the routine care in the three hospitals, once enrolled, samples collected as routine practice will be tested with mycobacterial culture in addition to Xpert. If needed, in case there is no enough sample volume remaining for culture after Xpert or if only one sample was collected because the first sample is Xpert positive, an additional respiratory sample will be collected (sputum or GA) and tested with Mycobacterial culture. The nurse will also record symptoms, refer the child for clinical exam and for chest X-ray, and collect stool samples. HIV-testing will be offered for children with unknown HIV-status. The two stool samples and additional respiratory samples if necessary will be collected for the purpose of the study only. However, culture and drug susceptibility results from the respiratory samples will be made available to the clinician for case management.

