7. STUDY PROCEDURES

7.1. Selection process

7.1.1. Prospective cohort

Children from the TB-Speed studies:

Study nurses from the TB-Speed SAM and TB-Speed HIV studies will identify potential eligible cases based on the selection criteria of having presumptive TB (all children enrolled in the TB-Speed HIV study and part of those enrolled in the TB-Speed SAM study) and will ask for the informed consent of the parent/guardian and assent of the child older than 7 years. This will be an additional consent and assent for co-enrolment in the TB-Speed stool processing study.

Children from the routine practice:

The nurses from the ward will be informed about all the TB-Speed studies taking place in the hospital wards and will inform the TB-Speed study nurse for any potentially eligible child. If the child is eligible for the TB-Speed HIV or SAM study, he will be proposed to participate to these studies first. Then, the participation in the stool processing study will be proposed secondarily for those who accepted to be part in the TB-Speed HIV or SAM study. Children that will not be eligible for the HIV or SAM studies will only be offered participation to the stool processing study. After verification, the study nurse will ask the parent/guardian's informed consent and the child's assent if older than 7 years.

7.1.2. Enrichment cohort:

Children from the TB-Speed studies:

Study nurses from the two TB-Speed Studies will identify potential eligible cases among those who are Ultrapositive on respiratory samples based on the selection criteria and will ask for the informed consent of the parent/guardian and assent of the child older than 7 years.

Children from the routine practice:

Because respiratory sample collection is not systematically collected in children with presumptive TB in the pediatric wards, the nurses from the ward will be informed about the study and will inform the study nurse when a child presents with a positive Xpert result. After verification, the study nurse will ask for the informed consent of the parent/guardian and assent of the child older than 7 years to complete the enrolment.

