9.5. Responsibilities of the investigators

The investigators are responsible for:

- Grading the severity of AEs occurring from GA collection reported by study nurses as severe or potentially life-threatening
- Reporting SAEs, to the sponsor and to the appropriate country authorities.
- Assessing the causality of all SAE in relation to the study intervention and to concomitant intervention/medication.

The assessment on expectedness will be done by the sponsor.

SAEs, as defined above, should be reported as soon as they are known to the country CTU according to the last updated SOP. A specific "SAE report form" will be used. SAEs will be reported immediately by the country CTU to the INSERM Pharmacovigilance Department according to appropriate SOPs. If needed, queries on SAEs will be sent to the investigators by the INSERM Pharmacovigilance Department representative.

All SAEs must be reported if it they occur in a participant:

- from the date of signature of the informed consent to the study;
- during the follow-up of the participant scheduled by the study;
- until 4 weeks after the end of follow-up when it still could be related to the study intervention.

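### Sections 9.1, 9.4 and 9.5 give different scopes for SAE reporting, so a serious but not life-threatening event from a study-performed gastric aspiration has no clear route to the sponsor

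*Protocol*

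**What the plan says.** Section 9.1 gives six seriousness criteria: death, threat to life, hospital admission or a longer stay ("Requires hospitalization or prolongation of existing hospitalization"), lasting disability, congenital anomaly, and an important medical event.

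Section 9.4 narrows what goes to the sponsor. It opens with its reasons, "In this diagnostic study without investigational medicinal product, and with very low expected risk of AEs linked to the intervention", and then states that "there will be no systematic notification of SAEs to the sponsor at the exception of" two categories: death, and "Life-threatening AEs, excluding asymptomatic biological AEs of grade 4". Relation to a study procedure plays no part in the rule.

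Section 9.5 makes investigators responsible for reporting SAEs to the sponsor and for judging the causality of every SAE. It says "All SAEs must be reported if it they occur in a participant" from consent until four weeks after follow-up, the last period applying to events that could still be related. It also refers back to an SAE definition given earlier without naming the section. Separately, investigators grade GA events that nurses report as severe or potentially life-threatening.

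On GA itself, section 9.2 says "Both GA and sputum collection are components of routine practice in the two hospitals participating in the study". Section 7.1.2, on routine recruits to the enrichment cohort, begins "Because respiratory sample collection is not systematically collected in children with presumptive TB in the pediatric wards". Section 4.2 says for the same group that "additional respiratory samples if necessary will be collected for the purpose of the study only".

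**The concern.** A site investigator who sees a child's stay prolonged after a study GA, without immediate danger to life, gets two answers. The plain wording of 9.5 with the 9.1 definition says to report it to the sponsor. Section 9.4 says it need not be notified.

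The sponsor's duties in 9.6.1 (recording SAEs, assessing causality, deciding whether a reaction was expected) work on the SAEs that investigators report. If 9.4 governs, the one study sampling procedure for which the protocol names an expected adverse event can produce serious harm that never enters that review. Section 15.3 also promises ethics committees information on serious or unexpected events likely to affect safety, which is harder to honour for events the sponsor does not receive.

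**Working it through.** The plan gives no figure to reproduce, and no arithmetic beyond a count applies. The check sets the passages side by side.

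**Step 1: the seriousness criteria against the two rules.**

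| Criterion in 9.1 | Notified under 9.4 | Reported under 9.5 if the 9.1 definition applies |
|---|---|---|
| Death | yes | yes |
| Life-threatening | yes (symptom-free grade 4 biological events excluded) | yes |
| Admission or longer stay | no | yes |
| Disability or incapacity | no | yes |
| Congenital anomaly | no | yes |
| Important medical event | no | yes |

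Section 9.4 keeps 2 of 6 criteria and leaves out 6 − 2 = 4. Of those four, a congenital anomaly is not a plausible result of GA, so three matter in practice.

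**Step 2: the two readings of 9.5.** If its back-reference means 9.1, the section headed as definitions, then 9.4 and 9.5 contradict each other on four criteria. If it means the shorter list in 9.4, the sections agree, but a serious procedure-related event outside that list has no stated route to the sponsor. Each reading leaves something to correct.

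**Step 3: is GA a study procedure?** In part.
- Table 3 (section 7.3) codes GA or sputum for routine recruits as both research and routine care. The study does it when it is not already in the chart.
- Section 4.2 allows an additional sputum or GA, for study purposes only, in routine recruits to the enrichment cohort when volume is short or only one sample was taken.
- Section 7.8.1 has study nurses perform GA.
- Section 9.2 itself places vomiting after GA under the adverse events expected from the study intervention.
- Against this, section 4.2 describes Ultra testing of stage 1 respiratory samples as routine, and section 7.2 says children co-enrolled from the HIV and SAM studies have only stools added.

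Some GAs are therefore done for the study, and the number cannot be read from the protocol.

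**Step 4: what happens to a severe GA event.** Under 9.5 the nurse reports it and the investigator grades it. If it is life-threatening, 9.4 sends it on. If it is serious but not life-threatening, 9.4 sends it nowhere, and 9.6.1 does not reach it.

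**Step 5: number of hospitals.** Section 9.2 refers to two hospitals, while sections 5.2 and 7.8.1 give three.

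**The case against.** The strongest reply is that 9.4 makes a declared and reasoned choice. A diagnostic study without a product may limit what it notifies, and 9.4 is the specific rule on the subject. The back-reference in 9.5 comes straight after the 9.4 list, and the sentence about all SAEs introduces a reporting window, so it can be read as fixing when to report and not what. An SOP and a dedicated form, neither of which is shown, may settle the scope. On that view only a wording fix is needed.

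Much of this stands. Restricted notification is legitimate, and the reconciling reading is available. But that reading does not close the gap in step 4: it confirms that serious GA-related events short of life-threatening are left out. The protocol asks investigators to grade such events and then gives them no destination.

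A reader might go further in four ways that the documents do not support.
- **That notification was cut because GA is routine care.** Section 9.4 cites the absence of a product and the low expected risk. The routine-practice sentence is in 9.2, and 9.4 does not refer to it.
- **That these events go unrecorded.** Section 9.3 drops systematic reporting of other adverse events, but section 10.1.1 lists adverse events among the data collected and section 10.3.5 has them coded.
- **That new-fact reporting also depends on notified SAEs.** Section 9.1 defines a new fact by any relevant safety data, and 9.6.2 binds both sponsor and investigator.
- **That a number of missed events can be given.** The protocol states neither a rate of serious events after GA nor a count of study-performed GAs.

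**Conclusion.** The point holds as an inconsistency of scope with one practical consequence. Four of the six criteria in 9.1 are outside 9.4 and inside the plain wording of 9.5. Under 9.4, a serious but not life-threatening event from a study-performed GA has no stated path into the sponsor's causality and expectedness review. The consequence is confined to GAs done for the study in routine recruits, and its frequency cannot be estimated from the protocol. The conclusion assumes that no unseen SOP already notifies such events. Even if one does, the protocol should say so. The accuracy estimates are unaffected. The change is worth making because it alters what the sponsor sees, so it is more than editorial.

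**What to change.** Reconcile sections 9.1, 9.4, 9.5 and 15.3 in one short amendment:
- **9.4:** add a third exception, so that any event meeting a 9.1 criterion and considered possibly related to a study-performed sampling procedure is notified to the sponsor.
- **9.5:** replace the reference to all SAEs with SAEs notifiable under 9.4, and name the section that the back-reference points to.
- **15.3:** align the duty to inform ethics committees with the same scope.
- **9.2:** say that some GAs are done for the study, and correct the number of hospitals to three.

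Hospital admissions due to the child's underlying illness remain outside notification, as the protocol intends. The cost is the amendment, an update of the SAE SOP and a few extra SAE forms.
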